10.3 Analysis Sets

For the purposes of analysis, the following populations are defined:

Population	Description
Enrolled	All participants who sign informed consent and are registered in IRT
Treated	All participants who received any amount of study intervention
Randomized	All participants who were randomized using IRT
Randomized PD-L1 \geq 1%	All participants who were randomized using IRT with \geq 1% PD-L1 tumor expression
Safety-evaluable	All randomized participants who have received study intervention (all 3 components) and have completed the safety-evaluation period of 12 weeks, or who discontinued any study intervention due to toxicity prior to completing the safety-evaluation period.
PK	All participants who received at least 1 dose of study intervention and had any available concentration-time data
Immunogenicity	All treated participants who have baseline and at least 1 post-baseline pre-infusion immunogenicity assessment

Abbreviations: IRT, interactive response technology; PD-L1, programmed death-ligand 1; PK, pharmacokinetic.

10.4 Statistical Analyses

The SAP will be developed and finalized before database lock and will describe the selection of participants to be included in the analyses and procedures for accounting for missing, unused, and spurious data. Below is a summary of planned statistical analyses of the primary and secondary

endpoints. A description of the participant population will be included in a statistical output report including subgroups of age, gender, and race.

10.4.1 General Considerations

10.4.1.1 Propensity Score Method to Select Control Data from Historical Trial

One downside of using historical control data augmentation for the current control arm in randomized controlled trials is potential discrepancies in prognostic factors between the historical data and the current control arm. One approach to minimize the bias is to use the Propensity Score Method to select historical data that are similar in terms of the observable pre-treatment characteristics with participants in the current study. All participants treated with nivolumab plus ipilimumab in CheckMate 227 and Study CA020016 will be combined and fit by logistic regression model using prognostic factors (eg, histology, PD-L1 expression, tobacco use, performance status, age, and gender) as independent variables, and the group assignment to the historical or the current study (0 = historical trial, 1 = the current study) as response variable. The 1:1 Greedy Nearest Neighbor Matching algorithm will be used to select about 180 participants from the CheckMate 227 study who are similar to the randomized participants from Arm B in Study CA020016 at the levels of baseline covariates mentioned above (see [Appendix 10](#)).

10.4.1.2 Bayesian Augmented Control Design

Hazard ratio between treatment and control arm will be estimated by a Bayesian exponential likelihood model with BAC arm as follows:

$$\lambda_i = \lambda e^{\theta I_i}$$

where

- λ_i is the hazard rate corresponding to the treatment arm for the i th participant;
- λ is the hazard rate for the current control arm.
- I_i is an indicator variable equal to 1 if the i th participant in the group received the current experimental arm and 0 otherwise;
- θ is the log hazard ratio (HR) between the current experimental arm and the current control arm

We assign a weak normal prior to log HR assuming no treatment effect as a priori. The prior for control hazard rate λ is assumed to follow a gamma (α , β) distribution where alpha is used to gauge the borrowed effective number of events from historical data and alpha/beta is the hazard rate estimated from the selected historical control data after propensity score matching from the CheckMate 227 study (see [Appendix 10](#)).⁴¹ The detailed implementation is discussed in the SAP.

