5.4.6 Rationale for Stratification

To minimize the potential for imbalances across treatment arms, there will be 2 stratification factors utilized in this trial: histology (squamous versus nonsquamous) and tumors PD-L1 expression (< 1%, 1% - 49%, ≥ 50%).

The prognostic implications of histology are well established, even before the advent of immunotherapy, hence different chemotherapy regimens are indicated according to histology.

With regard to PD-L1 expression, previous clinical studies with nivolumab monotherapy have shown participants with PD-L1 positive tumors may have better outcomes with PD-1-based therapies than those with nonexpression. In the CheckMate 227 study, PD-L1 status may impact response to treatment with nivolumab plus ipilimumab (see [Table 5.4.2-1](#)). Participants in the current trial will therefore be stratified by PD-L1 status as the effect of PD-L1 expression on response to anti-PD-1, anti-CTLA-4, and anti-TIGIT combination therapies is not yet known.

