10.2 Sample Size Determination

The sample size of the study is calculated to have a sufficient probability of making the correct decision and have a low probability of making an incorrect decision under the pre-defined go criteria of primary efficacy endpoint of PFS in the PD-L1 $\geq 1\%$ subgroup. Using a Bayesian augmented control (BAC) design, a portion of the control cohort for Study CA020016 will be

borrowed from participants treated with nivolumab plus ipilimumab in Study CheckMate 227 whose baseline prognostic factors are similar to the current randomized population. Based on the results in the CheckMate 227 study, it is assumed that the median PFS in Arm B is 5 months with a constant HR of 0.605 of Arm A vs Arm B for the PD-L1 $\geq 1\%$ subgroup. The pre-defined go criteria at the end of the trial is probability (Pr) (HR < 1) > 0.9 and Pr (HR < 0.7) > 0.5. With the above assumption, 64 PFS events will need to be observed across the 2 arms, and there is 72.2% probability of making a go decision for a scenario at the interim analysis occurring at about 70% of the events, and 78.1% probability of making a go decision at the final analysis. This assumes 12 months for accrual and a minimum of 10 months follow up, for a total of 105 randomized participants with PD-L1 $\geq 1\%$ expression, with approximately 180 participants randomized under current assumptions of prevalence in the primary subgroup. The participants will be randomized to the BMS-986207 with nivolumab plus ipilimumab (Arm A) and the nivolumab plus ipilimumab (Arm B) in a 2:1 ratio.

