The sample size of the study is planned to ensure a sufficient probability of making the correct decision and a low probability of making an incorrect decision under the pre-defined go criteria for the primary objective and is based on assumptions of expected prevalence of PD-L1 expression in the different PD-L1 subgroups. To ensure the randomized population is representative of the NSCLC population and to allow for appropriate subgroup analyses, total enrollment may be adjusted to ensure at least 105 randomized participants with tumor cell PD-L1 expression $\geq 1\%$, at least 75 randomized participants with tumor cell PD-L1 expression 1% - 49%, and at least 75 randomized participants with tumor cell PD-L1 expression < 1%, based on central laboratory results. The operating characteristics based on simulation under various scenarios are listed in Table 10.2-1 and Table 10.2-2. The simulation is conducted with FACTS 6.2 software (Berry Consultants, LLC).⁴⁰

Table 10.2-1: Operating Characteristics of Design Performance Under Different Sample Size, Borrowed Events, and Assumed True Hazard Ratios in the PD-L1 Expression $\geq 1\%$ Population

Historical Control		Current Control (mPFS)	Assumed True HR	N = 105 (2:1)		N = 90 (2:1)	
Historical Control (mPFS)	Borrowed Effective Events			Go%	No-go%	Go%	No-go%
			1	2.1%	90.0%	3.9%	88.4%
	14		0.7	49.1%	24.4%	51.9%	24.6%
5 months		5 months	0.6	79.3%	6.3%	77.9%	8.8%
			1	5.6%	84.4%	7.5%	81.9%
	1		0.7	49.0%	28.2%	50.8%	28.4%
			0.6	74.9%	10.7%	73.0%	13.1%

Abbreviations: HR, hazard ratio; mPFS, median progression-free survival; PD-L1, programmed death-ligand 1.

Table 10.2-2: Operating Characteristics of Design Performance Under Different Sample Size, Borrowed Events, and Assumed True Hazard Ratios in the All Randomized Population

Historical Control		Current Control (mPFS)	Assumed True HR	N = 180 (2:1)		N = 150 (2:1)	
Historical Control (mPFS)	Borrowed Effective Events			Go%	No-go%	Go%	No-go%
			1	0.3%	93.1%	0.6%	92.0%
	30		0.7	48.7%	11.1%	50.6%	15.7%
5 months		5 months	0.6	86.6%	1.4%	84.9%	2.2%
			1	1.6%	90.3%	2.8%	87.9%
	1		0.7	48.2%	21.4%	50.1%	23.9%
			0.6	80.4%	4.6%	79.5%	7.1%

Abbreviations: HR, hazard ratio; mPFS, median progression-free survival.

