10.4.2 Primary Endpoint(s)

Table 10.4.2-1: Primary Endpoints

Primary Endpoint	Description	Timeframe
PFS by BICR in the PD-L1 $\geq 1\%$ population is defined as the time from randomization to the date of the first documented tumor progression by BICR or death from any cause.	The PFS curve will be estimated using the Kaplan-Meier product-limit method. A primary analysis will be based on the BAC study. A sensitivity analysis will be based on log-rank test stratified by the PD-L1 expression ($< 1\%$, $1\% - 49\%$, $\geq 50\%$) and histology will be used to compare PFS based on RECIST v1.1 by BICR between the 2 treatment arms. HR and corresponding 2-sided 95% CI for PFS primary endpoint analysis and 95% CI will be estimated using a Cox proportional hazard model, with treatment arm as a single covariate, stratified by above PD-L1 expression and histology to assist in interpretation of the PFS analysis.	Time from randomization and every 6 weeks after randomization for the first 48 weeks, then every 12 weeks, until progression (by BICR), death, study discontinuation or initiation of subsequent therapy

Abbreviations: BAC, Bayesian augmented control; BICR, blinded independent central review; CI, confidence interval; HR, hazard ratio; PD-L1, programmed death-ligand 1; PFS, progression-free survival; RECIST, Response Evaluation Criteria in Solid Tumors.

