APPENDIX 10 DETAILS OF THE PROPENSITY SCORE MATCHING AND BAYESIAN AUGMENTED CONTROL (BAC) ANALYSIS

1.1 Propensity Score Matching

The use of historical control data as synthetic control for single-arm trial or augmentation for the current control arm in random controlled trials becomes promising in boosting the statistical power and estimate accuracy in the recent development of clinical trial design and practice. One downside of this method is potential discrepancies in prognostic factors between the historical data and the current active or control arm. With the availability of individual patient level data from historical controls, one approach to reduce biases is to use the Propensity Score Method to select historical data that are similar as participants from the active trials. The propensity score approach we employ in this protocol includes the following steps:

1. Selection of covariates or prognostic factors in multivariate logistic regression model

The variables for the propensity score modeling are selected based on prior clinical knowledge and their availability in the historical trial (CheckMate 227).

2. Propensity score matching

In the logistic regression model for the propensity scoring, the dependent variable is the indicator whether the patient belongs to the historical trial or the current trial, and the independent variables are the baseline covariates/prognostic factor mentioned above. The Greedy Nearest Neighbor Matching will be used to select about 180 control participants from the historical arms (1:1 matching ratio).¹ The matching caliper is set to 0.2 as appropriate so that participants are matched only if the difference in the logits of the propensity score for pairs of participants from the 2 groups is less than or equal to 0.2 times the pooled estimate of the common standard deviation of the logits of the propensity scores.

3. Assessment of Balance between Historical and Current Control

The frequency of all the binary covariates will be tabulated for the historical and current control participants before and after propensity score matching to assess the improved balance.

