1.2 Bayesian Modeling for Augmented Control with Historical Data

A Bayesian exponential-likelihood model has the following form:

$$\lambda_i = \lambda e^{\theta I_i}$$

where

- λ_i is the hazard rate corresponding to the treatment arm for the i th participant;
- λ is the hazard rate for the current control arm.
- I_i is an indicator variable equal to 1 if the i th participant in the group received the current experimental arm and 0 otherwise;
- θ is the log hazard ratio (HR) between the current experimental arm and the current control arm

For prior specification, we assign a normal prior to θ (log HR) where $\mu = 0$ and $\sigma = 100$, assuming no priori treatment effects, and weakly informative prior with large variation:

$$\theta \sim N(\mu, \sigma^2)$$

The hazard rate for control arm is augmented by informative prior specified by Gamma distribution:

$$\lambda \sim \text{Gamma}(\alpha, \beta)$$

which can be re-parameterize to:

$$\lambda \sim \text{Gamma}(n, \frac{n}{\mu})$$

with

$$\alpha = n, \beta = \frac{n}{\mu}$$

where μ is the control hazard rate from the historical control selected by the Propensity Score Method assuming exponential distribution, and n is approximately the effective number of events this informative prior is equivalent to.^{2,3}

REFERENCES:

- ¹ Rosenbaum PR. Observational studies. New York: Springer-Verlag; 2002. (Available upon request)
- ² Smith CL, Thomas Z, Enas N, et al. Leveraging historical data into oncology development programs: Two case studies of phase 2 Bayesian augmented control trial designs. Pharm Stat 2020;19:276-90.
- ³ FACTS 6.2: Fixed and Adaptive Clinical Trial Simulator. Berry Consultants. Available from: URL: www.berryconsultants.com.

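### The primary BAC model omits the PD-L1 and histology strata; the attenuation is small, but the go probability depends, in either direction, on the PD-L1 mix of the matched historical controls

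*Combined protocol and SAP*

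**What the plan says.** Section 10.4.1.2 introduces the primary model: "Hazard ratio between treatment and control arm will be estimated by a Bayesian exponential likelihood model with BAC arm as follows". The formula gives each participant the hazard λ, multiplied by exp(θ) in Arm A. The prior on λ is a single Gamma distribution in which "alpha is used to gauge the borrowed effective number of events from historical data"; its mean is the hazard of the matched CheckMate 227 controls. Appendix 10 section 1.2 repeats this and gives θ a normal prior with standard deviation 100, "assuming no priori treatment effects, and weakly informative prior with large variation". Neither place has a PD-L1 or histology term. Section 10.4.1.2 leaves detailed implementation to a separate SAP, whose text is not in the reviewed document.

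Both factors stratify the randomisation. Section 5.4.6 gives a reason: "In the CheckMate 227 study, PD-L1 status may impact response to treatment with nivolumab plus ipilimumab". They also enter the supporting analyses without borrowing. Table 10.4.2-1 says "A sensitivity analysis will be based on log-rank test stratified by the PD-L1 expression" and histology, and adds a stratified Cox model. Section 10.4.1.3 describes an unaugmented log-rank test without mentioning strata.

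The strata are used in selecting the historical controls. Section 10.4.1.1 lists histology and PD-L1 among the propensity covariates, and Appendix 10 section 1.1 sets 1:1 greedy matching with a caliper of 0.2. The balance check there reads: "The frequency of all the binary covariates will be tabulated for the historical and current control participants before and after propensity score matching". It gives no threshold and no action if imbalance remains.

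**The concern.** The primary population (PD-L1 1% or more) contains two randomisation categories whose historical control medians differ, so one exponential hazard is unlikely to describe it. Two consequences follow.

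- Pooling strata with different hazards pulls the estimated HR towards 1.
- The prior mean is an average over whatever PD-L1 mix the matched set happens to have. If that mix differs from the trial's, the borrowed control hazard is wrong for the trial, and the go decision moves with it.

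A mix difference is built into the design. Sections 5.2 and 10.2 require at least 75 participants at 1%-49%. With 105 in the primary population, that is 75/105 = 71%. In the CheckMate 227 nivolumab plus ipilimumab arm it was 191/396 = 48%. Matching has to close that gap.

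The planned sensitivity analyses cannot isolate the effect of borrowing. They drop borrowing and change the model together, and in Table 10.4.2-1 they also add stratification.

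**Working it through.** **Inputs.** From Section 10.2: 105 participants at 2:1 (70:35), control median 5 months, HR 0.605, 12 months of accrual plus 10 months of follow-up (cut at month 22), and the go rule "probability (Pr) (HR < 1) > 0.9 and Pr (HR < 0.7) > 0.5". From Table 10.2-1: 14 under "Borrowed Effective Events". From Table 5.4.2-1: control medians 4.01 and 6.74 months. Assumed: exponential PFS within strata, no dropout, and a historical hazard fitted over the same 10 to 22 months of follow-up.

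**Formula, single-hazard model.** With θ's prior flat in effect, Arm A's hazard is Gamma(d_A, T_A) and the control hazard is Gamma(n + d_C, n/μ + T_C), where d is events and T is person-time. Hence

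Pr(HR < h) = F[ h·T_A·(n + d_C) / (d_A·(n/μ + T_C)) ], with 2d_A and 2(n + d_C) degrees of freedom.

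**Formula, stratified model.** With λ_s integrated out,

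L(θ) ∝ Π_s exp(θ·d_As) / (n_s/μ_s + T_Cs + e^θ·T_As)^(n_s + d_Cs + d_As), evaluated on a grid of θ.

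**Step 1: reproduce the plan.** With n = 14 and μ = ln 2/5, final go at HR 0.605 is 78.1% (stated 78.1%). The 105-participant, 14-event cells of Table 10.2-1 come out at 2.2%, 50.4% and 79.5% go for HR 1, 0.7 and 0.6 (stated 2.1%, 49.1% and 79.3%). The match needs the month-22 cut, with about 82 expected events. A cut at exactly 64 events gives 75.1%.

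**Step 2: PD-L1 heterogeneity.** Hazards are ln 2/4.01 = 0.173 and ln 2/6.74 = 0.103 per month, a ratio of 1.68. Expected Arm B events are 31.1, so the prior's share of control information is 14/(14 + 31.1) = 31%.

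**Step 3: attenuation.** Set the matched mix equal to the trial mix (71% at 1%-49%). The single-hazard model gives go 77.3% and median HR 0.608 (0.612 asymptotically, without the prior). The stratified model gives 78.6% and 0.602. The loss is 78.6 − 77.3 = 1.3 points. Go at HR 1 is 2.1% under both.

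The documents give no histology effect or squamous share. Assuming 30% squamous and a histology hazard ratio of 1.3, 1.5 or 2.0, go is 76.0%, 75.5% or 73.5% with the single hazard, against 77.9%, 77.9% or 77.7% stratified.

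**Step 4: mix error.** Single-hazard model, trial mix held at 71%:

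| Matched share at 1%-49% | Go, HR 0.605 | Go, HR 1 |
|---|---|---|
| 48% (unmatched CheckMate 227) | 70.6% | 1.1% |
| about 10 points below the trial | 74.6% | about 1.6% |
| 71% (equal to the trial) | 77.3% | 2.1% |
| about 10 points above the trial | 80.0% | 2.8% |
| 100% | 83.9% | 4.2% |

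A repeat run of 40,000 trials per cell agreed within 0.6 point. At matched shares of 30%, 48% and 100%, the stratified model stays at 78.4-78.8%, with 2.1-2.4% at HR 1. For scale, borrowing 14 events rather than 1 gains 79.3 − 74.9 = 4.4 points at HR 0.6 in Table 10.2-1.

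**Step 5: how likely is a mix error?** Matching was simulated with the Table 5.4.2-1 counts and assumed distributions for the other covariates. With PD-L1 entered as three categories, the matched share at 50% or more was off by 0-1 point on average. The SD was 1.5-3.3 points when all 180 participants were matched and 2.6-6.6 points when only Arm B was. Errors above 10 points occurred in 0-0.3% and 0.3-15% of runs respectively. In a separate Arm B simulation, an ordinal score left that share 7 points too high on average, and a binary split at 1% left it 24 points too high.

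**The case against.** The best defence is that the strata are not ignored. PD-L1 and histology are named propensity covariates and a caliper applies. A 71% against 48% difference would make PD-L1 a strong predictor of trial membership, so the score would act on it. That stands: with PD-L1 entered as categories, the 70.6% case is very unlikely and a 10-point error is a tail event. The protocol does not state the coding, however, and it also leaves unclear who is matched: about 180 historical controls at 1:1 does not fit an Arm B of about 60.

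Second, the attenuation is close to trivial, and part of it is the difference between a marginal and a conditional HR, which is a choice of estimand. That stands too.

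Third, the PD-L1 contrast is estimated. The 95% intervals, 2.99-5.52 and 4.53-11.01 months, overlap, and a smaller true contrast would shrink every mix effect shown.

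Fourth, within the primary population PD-L1 has two levels, and a three-level factor can be coded as binary indicators. A balance table of binary covariates could therefore include it. The text does not exclude this, but does not ensure it.

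Fifth, crossing PD-L1 with histology would be too sparse: 14/4 = 3.5 borrowed events per cell on average, with about 35 − 25 = 10 Arm B participants at PD-L1 50% or more. That is right, and the fix avoids it.

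**Conclusion.** The concern holds as a residual risk worth closing. The single-hazard model costs about 1 point of go probability through PD-L1 and does not inflate false-go. Its more important weakness is that the go probability follows the matched PD-L1 mix: about 2.5-3 points for a 10-point error, with false-go between about 1.6% and 2.8%.

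A reader might infer that the primary HR is materially biased towards 1, or that go probability will drop to about 70%. The documents support neither. The attenuation is about 0.003-0.007 on the HR from PD-L1 alone. Mix error can act in either direction: too many historical controls at 50% or more raise the HR, and too many at 1%-49% lower it and raise false-go. The 70% figure requires matching to leave PD-L1 unchanged.

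The sizes rest on exponential PFS within categories, the Table 5.4.2-1 medians, a 75/30 split, no dropout and the month-22 cut.

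**What to change.** In Section 10.4.1.2 and Appendix 10:

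- Use PD-L1-category-specific control hazards with a common θ: λ_s ~ Gamma(n_s, n_s/μ_s). The n_s sum to n and are allocated in proportion to matched historical events; μ_s comes from matched CheckMate 227 participants in that category. Use two categories for the primary population and three for all randomised participants.
- Enter histology as a covariate rather than crossing it with PD-L1.
- Match exactly on PD-L1 category, and tabulate every PD-L1 level in the balance check.
- Add the same stratified model with n = 1 as a sensitivity analysis, so that only borrowing differs from the primary.
- Re-run Table 10.2-1 for the final specification.

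This needs changes in wording and one re-simulation. The strata are already recorded in the IRT, and no new data or participants are needed. The downsides are a slightly more complex model and possibly fewer matched historical participants. The change should be fixed before by-arm efficacy data are seen.

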10.4.1.3 Sensitivity Analyses

Sensitivity analyses will be conducted using frequentist log-rank test for HR of control and treatment arms for PFS without augmentation by historical control data.

10.4.2 Primary Endpoint(s)

Table 10.4.2-1: Primary Endpoints

Primary Endpoint	Description	Timeframe
PFS by BICR in the PD-L1 $\geq 1\%$ population is defined as the time from randomization to the date of the first documented tumor progression by BICR or death from any cause.	The PFS curve will be estimated using the Kaplan-Meier product-limit method. A primary analysis will be based on the BAC study. A sensitivity analysis will be based on log-rank test stratified by the PD-L1 expression ($< 1\%$, $1\% - 49\%$, $\geq 50\%$) and histology will be used to compare PFS based on RECIST v1.1 by BICR between the 2 treatment arms. HR and corresponding 2-sided 95% CI for PFS primary endpoint analysis and 95% CI will be estimated using a Cox proportional hazard model, with treatment arm as a single covariate, stratified by above PD-L1 expression and histology to assist in interpretation of the PFS analysis.	Time from randomization and every 6 weeks after randomization for the first 48 weeks, then every 12 weeks, until progression (by BICR), death, study discontinuation or initiation of subsequent therapy

Abbreviations: BAC, Bayesian augmented control; BICR, blinded independent central review; CI, confidence interval; HR, hazard ratio; PD-L1, programmed death-ligand 1; PFS, progression-free survival; RECIST, Response Evaluation Criteria in Solid Tumors.

